Secondary outcome variables will include blood pressure, serum LDL, diabetes quality of life measured by the self reported Diabetes Distress Scale, and depression assessed with the PRIME-MD Patient Health Questionnaire (PHQ-9). All secondary outcomes will also be measured at baseline, 6 months and 12 months.

K. Study Design and Methods:

1. Is this a clinical trial? YES NO
 1.1. If yes, what type? Check all that apply.
 Phase I Phase II Phase III Phase IV
 1.2. If yes, this study must be registered on Clinicaltrials.gov.

2. Design

2.1. What research methods will be used in the project? Check all that apply.

 Surveys/Questionnaires	 Interviews	 Audio Taping
 Behavioral Observations	 Chart Reviews	 Video Taping
 Focus Groups	 Randomization	 Double-Blind
 Control Group	 Placebo	 Withhold/Delay Treatment
 Specimen Collection	 Deception	 Telephone Survey
 Other (Describe)		

[figure not shown]
2.2. Describe how randomization or other treatment assignment will be made.

After informed consent is obtained and the baseline interview is complete, participants will be randomized. Randomization will be a staged process (see figure 1). For both steps, randomization will be conducted by the study statistician using a random number generator and via permuted block randomization with variable block size to force balance among treatment group assignments after every block of participants is enrolled.

At stage 1, interested participants will be randomized to usual care or peer mentoring. At stage 2, interested participants will be randomized to usual care or peer mentoring from a former mentee (FFM). In addition, former mentees will be randomized to either becoming a mentor or usual care (i.e. mentee assigned or no mentee assigned).

To date we have been randomizing patients in a 1:1 manner. After receiving IRB approval for this modification we will change to 2:1 randomization (2 to an intervention arm for every 1 enrolled into usual care). See below for exact numbers.

Figure 1 Randomization

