Data Collection: All participants (mentors and mentees) will complete a baseline survey, a short call at 1 and 3 months, a 6 month survey, a 12 month survey, a blood draw at baseline, 6 months, and 12 months and will have their medical health record under electronic review for an additional 6 months after the last in-person visit. Those randomized to arm 2 and further randomized to arm 4 will receive additional short calls at 7 months and 9 months and have one additional in person visit with blood draw at 18 months. A sample of mentors and mentees from stage 1 and stage 2 will be asked to complete qualitative interviews baseline, 6, 12, 18 months. Table 1 identifies data to be collected at each time point and the source of the data.

Table 1: Measurement Schedule							
	Baseline	1 M	3 M	6 M	12 M	18 M	24 M
Dependent Variables							
HbA _{1c} (blood)	x			x	x	x	
Blood Pressure (in person measurement)	x			x	x	x	
Direct LDL (blood)	x			x	x	x	
DM quality of Life (self-report) - Distress	x			x	x	x	
Depression Symptoms (self-report) - Mood	x			x	x	x	
Intervening Variables of Interest							
Social Support	x			x	x	x	
Self-Efficacy (self-report)	x			x	x	x	
Perceived Benefits and Barriers (self-report)	x			x	x	x	
Self-management Behaviors (self-report)	x			x	x	x	
Past Mentoring Dose Received by Current Mentor (Past records)	x						
Mentor's past Change in HbA _{1c} (Past study records)	x						
Mentee's assessment of mentor quality (self-report)				x	x	x	
Potential Confounders							
Demographics (self-report)	x						
Attachment Style (self-report)	x						
Perceived Need for Support (self-report)	x			x	x	x	
BMI (in person measurement)	x			x	x	x	
DM Health History (self-report)	x						
General Health History (self-report)	x			x	x	x	
Potential Contamination (self-report)				x	x	x	
Hypoglycemic Symptoms (self-report)	x	x	x	x	x	x	
Qualitative Perceptions of Program (self-report)	x			x	x	x	
Medical Record Review (Electronic medical record)**						x	x
* Current Mentoring Dose Provided by Mentor will be assessed monthly. For Ease of Presentation we did not include all collection times.							
** Exact timing of EMR review depends on arm – only reviewed once either at 18 or 24 months.							

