For self-reported data we will use validated survey questions developed by the PI or other researchers in the field. The research coordinator will be trained to measure BP and pulse rate at each visit using an automatic digital blood pressure monitor on the non-dominant arm after the subject has been seated for 5 minutes. An average of two measurements will be used for analyses. We will evaluate both change in systolic and diastolic BP as well as the percent of patients in each arm with ADA target BP (BP < 130/80 mmHG). Height and weight will be measured using standard procedures with a beam balance and a strain-gauge digital scale, respectively, and used to calculate body mass index (BMI).

We will conduct the qualitative interviews with the aim of understanding how, in terms of the outcome HbA_{1c}, successful mentor-mentee pairs differed from those who were not successful. Interview guides will be informed by *adult learning theory*. We will use semi-structured interviews. Open-ended questions will be followed by probes to prompt detail and ensure that a broad range of possible responses are elicited. Using constant comparison techniques, we will modify scripts in real time as new and unexpected themes emerge.

1.2. Explain if and how the follow-up of subjects will occur.

Follow-up will occur at 1 and 3 months post enrollment with a brief phone call, and at 6 months and 12 months post enrollment at the CMC VA Medical Center. Additional short calls at 7 and 9 months and an additional in person 18 month visit will also occur for those in arm 2 and 4. After follow-up in person visits are complete, all enrolled participants' medical health record will be under electronic review for an additional 6 months.

1.3. Describe where, how and who will be conducting study procedures.

Consent, study surveys and interviews, blood pressure measurements, and weight at baseline, 6 months, 12 months and when appropriate 18 months will occur at the CMC VA Medical Center and be performed by a project manager or research assistant.

One and three month hypoglycemic assessments will be assessed over the phone by a project manager or research assistant.

Evaluations of the serum HbA1c and LDL will be performed by the CMC VA Medical Center lab.

Electronic review of medical health records will occur at the CMC VA Medical Center on the VA server network.

1.4. If a survey study, specify the estimated amount of time that subjects will need to complete the questionnaires/tools.

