
The below table estimates the amount of time each step will require for data collection. The amount of time spent on mentoring calls is not determined by the study.

Table 2: Data Collection Step, Time to Complete and Mode of Collection		
Procedure	Estimated Time to Complete	Number of Times to Perform
Consent	30 minutes	1 (in person)
Baseline Survey	45 minutes	1 (in person)
Lab tests	10 minutes	3-4 (in person)
Hypoglycemic Symptoms	5 minutes	2 (phone call)
Follow-up Survey	30 minutes	2-3 (in person)
Qualitative Interviews	20 minutes	2-3 (in person)
Health record review	15 minutes	1 (electronically)
Mentor Training	60 minutes	1 (in person)
Reinforcement Calls	10-15 minutes	5 (phone call)
Estimated Total Active Time for Participants		
Arm 1	175 minutes (≈ 3.0 hours)	
Arm 2	385 minutes (≈ 6.5 hours)	
Arm 3	215 minutes (≈ 3.5 hours)	
Arm 4	385 minutes (≈ 6.5 hours)	
Mentors for Arm 2	325 minutes (≈ 5.5 hours)	

Based on experience, consent will take about 30 minutes and the baseline survey will take approximately 45 minutes. Follow-up visits will take about 30 minutes for survey completion and 20 minutes for the completion of qualitative interviews. The lab usually expedites tests for research and we expect patients will need to spend approximately 10 minutes getting their blood

drawn. The total time commitment for consent and data collection is estimated to be between 3 and 7 hours depending on the arm the person is in. However, given the time commitment we will reimburse participants \$50 for each in person visit to cover time and transportation costs and an additional \$40 for qualitative interviews if they agree to complete the qualitative interview portion of the study.

- 1.5. If a blood draw, specify the amount of blood to be drawn in milliliters and in teaspoonfuls or tablespoonfuls and specify how often and where the blood will be drawn.

Blood draws will occur at the CMC VAMC lab. We anticipate a maximum of 5ccs or 1 teaspoon of blood will be required for each in-person visit at baseline, 6 months, 12 months and when appropriate 18 months..

2. **Data Collection** (Include all questionnaires and survey tools with the submission.)

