2.1. Provide

- 2.1.1. the mode of data collection, e.g. telephone, in-person, questionnaire, interviews,

Data will be collected mostly by in-person survey, interview and lab tests. In addition, mentors will receive short reinforcement calls each month at which time we will collect data about how many times the mentor talked to the mentee in the month. Hypoglycemic symptoms will be assessed by phone at 1 and 3 months (additionally at 7 and 9 months for arms 2 and 4) . Electronic medical records will be reviewed 6 months after the last in person visit. See Table 1 and 2 for details.

- 2.1.2. the precise plan for how data is to be collected or acquired

Surveys will be read to participants and answers will either be directly input into a computer database or written onto paper forms and then transferred to a data base at a later time. The data base will reside on VA servers behind the VA firewall and will never be removed from the server. Paper records will be stored at CHERP behind an electronically locked entrance, a key-locked door and in a key-locked cabinet.

Qualitative interviews will also be read to participants and answers will be voice recorded. Interview data will be stored on the VA server and will be behind VA firewalls This data will be temporarily shared with Alpha Transcription, and University of Pennsylvania's Mixed Methods Research Lab, transcribing and coding respectively. Both companies are approved vendors with appropriate VA approved data security in place.

Data about the number of calls per month made by the mentor will be collected over the phone, and again responses will either be entered directly into a database or first onto paper and then into the database.

Data about hypoglycemic symptoms will be collected over the phone and responses will either be entered directly into a database or first onto paper and then onto the database.

Lab results will be obtained from the lab or via CPRS and entered into the secure research database.

Charts will be abstracted for additional HbA1c, LDL, and blood pressure readings 6 months after the last face-to-face visit.

- 2.1.3. exact location where data will be collected,

CMC VAMC and the CMCVAMC Annex (for in person, phone and chart derived data).

2.1.4. exact location where data entry will take place.

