2.1.3. Protocol modifications

If we desire to modify the protocol we will submit a modification to the IRB and not act on the modification until it has been approved.

3. **If applicable, define the plan for subjects if research shows results such as:**
 - 3.1. Depression **We will only use a depression screening tool and not assessing for depression. If the participant is willing and they screen positive for depression we will notify the participant's primary care provider.**
 - 3.2. Suicide **Will not be assessed**
 - 3.3. Abuse **Will not be assessed**
4. **Statistical Analysis**
 - 4.1. Include statistical power calculations and the assumptions made in making these calculations.

We will randomize 72 mentees from stage 1 to each arm of stage 2. To achieve 80% power to detect a 0.8 unit change in HbA1c, with standard deviation of 1.6, a sample of 64 patients per arm would be required. But to protect against possible attrition, we will inflate that by 10% and enroll 72 participants into each arm. Literature and guidelines suggest that an average decrease of 1 unit in HbA1c would provide a clinically meaningful improvement in health. We chose a 0.8 unit change to be conservative. We base our standard deviation of 1.6 on our pilot study and other studies of low control DM populations.

For stage 2 we will also randomize poorly controlled diabetics into mentoring or usual care arms. We will need 72 in the usual care arm (to be mentored by the 72 stage 1 mentees who become mentors). Since usual care for stage 2 can be combined with usual care for stage 1, there is no need for a 1:1 randomization. Initially, a 1:1 randomization was used, but after evaluation we

believe we can now switch to a 2:1 randomization to avoid recruiting more usual care patients than necessary. With this change we will enroll approximately 56 patients to usual care in stage 2.

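### U.3.2 gives no plan for a suicide-related answer, although the PHQ-9 is read aloud to participants; on the standard nine-item form a same-day response is needed

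*Combined protocol and SAP*

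**What the plan says.** Section J lists, among the secondary outcomes, "depression assessed with the PRIME-MD Patient Health Questionnaire (PHQ-9"), and adds: "All secondary outcomes will also be measured at baseline, 6 months and 12 months". Table 1 in M.1.1 carries the measure as "Depression Symptoms (self-report) - Mood". The Data Collection paragraph above that table applies the baseline, 6-month and 12-month surveys to mentors and mentees alike. Secondary aim 5 and H4 in U.4.2 use the mentor's baseline depression score as a predictor, so mentors are screened too.

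On mode, M.2.1.1 states: "Data will be collected mostly by in-person survey, interview and lab tests". M.2.1.2 states: "Surveys will be read to participants and answers will either be directly input into a computer database or written onto paper forms". On place and personnel, M.1.3 says that consent, surveys, interviews and measurements "will occur at the CMC VA Medical Center and be performed by a project manager or research assistant".

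U.3 is a form prompt, to be completed where applicable, asking what will be done for subjects if the research turns up depression, suicide or abuse. For depression (U.3.1), the protocol says that it screens rather than assesses, and that the primary care provider will be told if the screen is positive and the participant agrees. For suicide (U.3.2), the whole answer is "Will not be assessed". The abuse line (U.3.3) is answered the same way.

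**The concern.** A questionnaire read aloud puts a staff member in the room when each answer is given. If one of the questions concerns thoughts of death or self-harm, the study collects a suicide-related answer whether or not it calls this an assessment. The protocol would then be asking the question while stating no plan for a positive reply.

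The stake is participant safety. A person could tell study staff of self-harm thoughts and leave the visit without any step that the protocol requires. The HbA1c comparison is not touched.

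**Working it through.** No figure in the plan bears on this point, so the check is a comparison of the text, plus a count of administrations.

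**1. Can a suicide-related answer arise?** The documents name the PHQ-9 but do not print its items. *Assumption:* the form in use is the standard nine-item version, which includes an item on thoughts of death or self-harm. On that assumption the answer is yes, in every arm and among mentors, since the baseline survey comes before randomization (K.2.2) and all participants complete it (M.1.1). The U.3 prompt is then applicable.

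**2. How often is the question asked?**
- Section J: baseline + 6 months + 12 months = 3 per participant.
- Arms 2 and 4: 3 + 1 = 4 if the 18-month mark in Table 1 and the 18-month survey in the M.2.2 time line govern. Against this, section J stops at 12 months, and the H3 analysis in U.4.2 uses the depression score at 6 and 12 months only. The fourth administration is therefore uncertain.
- Stage 1 mentors: 3 by the Data Collection paragraph. The 12-month line of M.2.2 names only arms 1 to 4, so their third administration is less clear.

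These are opportunities for the question to be asked, not expected events. The documents give no basis for the share of positive answers, so no study-wide count is offered.

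**3. What does U.3.1 do for someone who gives a positive self-harm answer?** Its two conditions make four cases:

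| Overall screen | Willing to have provider told | Action under U.3.1 |
|---|---|---|
| Positive | Yes | Primary care provider notified; no timing stated |
| Positive | No | None |
| Negative | Yes | None |
| Negative | No | None |

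U.3.1 acts in one of the four cases. It states no cut-off for a positive screen and ties no action to a single item.

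**4. Does other text fill the gap?**
- S.1.2 (steps to minimize risk) deals with understanding of consent, voluntariness and confidentiality.
- U.1 deals with monitoring of hypoglycemia, and with review of serious adverse events by the principal investigator and reporting to the IRB and DSMB.
- U.2.1.1 deals with unanticipated problems: team review, immediate IRB reporting, and a halt if concerns are serious.

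These are oversight routes. None says what is done for the participant at the visit.

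**5. What could not be checked?** The instruction at M.2 reads "Include all questionnaires and survey tools with the submission", so the submission should have held the survey tools. U.4.2 also cites a Human Subjects section. Neither was available. The scripts mentioned in P.10.9 and V.5.1 are for consent and for recruitment calls, and are not where a survey-visit procedure would be expected.

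**The case against.** The strongest reply is that the conflict depends on something the documents do not show. No item of the PHQ-9 is printed, so the self-harm item is an assumption. That stands, and it makes the point conditional: if the form in use has no such item, U.3.2 may stay as it is.

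Second, the prompt asks for a plan only where applicable, and the reply may simply mean that suicide is not a study measure. The identical reply for abuse favors that reading, as does the line U.3.1 draws between screening and assessing. The reading is fair, but it does not close the gap. U.3.1 draws the same line and still gives a follow-up action, whereas U.3.2 gives none. Under the assumption the result can occur, so the prompt applies.

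Third, participants are not left with nothing. Visits take place at the medical center where they receive care, a physician investigator oversees the study, and primary care notification exists. This lowers the severity and makes a remedy easy, but it is not a written response at the visit.

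A reader might infer something stronger: that the study has no suicide-response procedure at all, or that staff would do nothing. The documents do not support that. The survey tools and the Human Subjects section were not available, and what is missing from this text is not thereby missing from the plan.

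**Conclusion.** The point holds conditionally and is worth acting on. Given the nine-item form, U.3.2 is not an adequate answer to the U.3 prompt, and the available text provides no same-visit response to a self-harm answer. A participant who gives one but screens negative overall, or who declines notification, is owed no action under U.3 as written.

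Two things must be true for the gap to be real: the form contains the item, and the unseen attachments contain no procedure. The sponsor can settle both from its own files. Confidence is medium for that reason.

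The size is 3 administrations per participant, possibly 4 in arms 2 and 4, with an unknown rate of positive answers. Enrollment began on September 27, 2012 and completion was anticipated by December 31, 2015 (K.3.3), so a change helps only visits still to come. It would be wrong to infer any effect on the trial's results: HbA1c, power and alpha do not depend on this.

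**What to change.** If the survey attachments or the Human Subjects section already hold a procedure, cite it in U.3.2. Otherwise replace U.3.2 with:

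*No formal suicide assessment is done. Staff check the PHQ-9 self-harm item before the participant leaves, and any positive answer is referred the same day to a VA clinician, whatever the total score and independent of the U.3.1 willingness condition, under a procedure approved by the IRB.*

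The rule should cover mentors as well as mentees.

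The cost is an IRB modification, brief staff training, a same-day referral route on visit days, and possibly consent wording to say that this referral does not wait on the participant's agreement. No item is added or removed, and no score or analysis changes.

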In order to assure 72 in each arm for stage 2, we will need a total of 144 mentees in stage 1. Again, to protect against possible attrition, we inflate that by 16% and enroll 171 mentees in stage 1. A corresponding number of mentors (171) will be recruited for stage 1. There will be no randomization of mentors in stage 1. Since usual care for stage 1 can be combined with usual care for stage 2, there is no need for a 1:1 randomization. Initially, a 1:1 randomization was used, but after evaluation we believe we can switch to a 2:1 randomization to avoid recruiting more usual care patients than necessary. With this change we will enroll approximately 139 patients to usual care in stage 1.

The combined number of poorly controlled diabetic patients receiving usual care will be approximately 195. The number of poorly controlled diabetic patients receiving peer mentoring will be 232 (171 in stage 1 and 72 in stage 2). The number of mentors in stage 1 will be 171, and the number of mentors in stage 2 will be 72 (from among those who received mentoring in stage 1). The total number of patients in the study will be 594.

A recent analysis of clinical data from the CMC VAMC and its surrounding CBOCs indicate that in the last year there were 1,248 patients who would have qualified to be mentees and 1,810 who would have qualified to be mentors.

4.2. Define plans for data and statistical analysis, including key elements of the statistical plan, stopping rules and endpoints.

For Stage 1: We will test these primary hypotheses using an unadjusted intent-to-treat analyses, i.e., with adjustment for only baseline HbA_{1c}. The primary tests will assess the significance of the coefficients associated with the treatment assignment in a longitudinal linear model of the repeated HbA_{1c} as a function of treatment, where the active group (peer mentoring) is compared to the control group via an indicator variable. Standard t-tests will determine whether a significant difference in HbA_{1c} improvement occurred between the treatment arm compared to the control arm. To account for the fact that we are doing multiple tests, we will use the Bonferroni method and consider a treatment to be significantly different than the control if the p-value is less than $0.05/2=0.025$.

| Stage 2 Analysis:

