H2. Compared to usual care, veterans who receive peer mentoring from former mentees will have improved glucose control as measured by HbA_{1c}, BP, LDL levels, DM quality of life, and depression scores: We will examine the effectiveness of the intervention at 6 months and further examine sustainability at 12 and 18 months. 18 month assessments will only be of HbA_{1c}, BP, and LDL levels as derived from the EMR. We will test these primary hypotheses using an intent-to-treat (ITT) analyses, i.e., including all patients who completed a baseline assessment, as randomized. We will use linear and random effects longitudinal models to perform the ITT comparisons at each of the follow-up visits. Our primary outcomes will be HbA_{1c}, BP, LDL levels, DM quality of life, and depression scores. Our models will include a random effect for patient. The models will include the following fixed effects: a main effect for follow-up visit (with baseline visit as the reference), intervention group, and their interactions. Tests of the interaction terms will be used to determine the ITT difference between groups with respect to change from baseline. To examine whether veterans who received peer mentoring from former mentees have improved glucose control, BP, LDL levels, DM quality of life, and depression scores compared to veterans in the usual care group at 6 months, compared to baseline, we will implement these random effects models with mentee HbA_{1c}, BP, LDL, DM quality of life score, or depression score as the dependent variable. The ITT test for effectiveness will be based on HbA_{1c} and will be two-sided, with

$\alpha=0.05$ and will be based on the magnitude and statistical significance of the time*intervention interaction term at 6 months. To examine sustainability of improvement in glucose control, BP, LDL levels, DM quality of life, and depression scores we will use the same test, but will examine the intervention group*12 month time interaction term. To examine sustainability of improvement in glucose control, BP, and LDL levels at 18 months we will again use the same test, but will examine the intervention group*18 month interaction term.

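### The allocation ratio changes from 1:1 to 2:1 within each stage, but the H1 and H2 models have no term for allocation period, so part of any drift over time enters the treatment estimate.

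*Combined protocol and SAP*

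**What the plan says.** Section K.2.2 (randomization) says allocation has been 1:1 so far and continues: "After receiving IRB approval for this modification we will change to 2:1 randomization". The new ratio is two intervention patients to one usual care patient. Section U.4.1 (power calculations) applies the change to each stage separately. For stage 1: "Initially, a 1:1 randomization was used, but after evaluation we believe we can switch to a 2:1 randomization". For stage 2: "Initially, a 1:1 randomization was used, but after evaluation we believe we can now switch to a 2:1 randomization". The reason given is that usual care can be combined across stages, so fewer usual care patients are needed.

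Section U.4.2, For Stage 1, specifies "unadjusted intent-to-treat analyses", which it explains as adjustment for baseline HbA1c and nothing else. Section U.4.2, Stage 2 Analysis (H2), lists a random effect for patient and fixed effects for visit, group and their interaction. It then adds baseline characteristics that differ between groups at the 0.20 level. It expects no confounding, because of stratified and blocked randomization, except what arises by chance. K.2.2 describes permuted blocks of variable size and names no strata. No model mentions allocation period or enrolment date.

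**The concern.** When the ratio changes part-way, assignment is random only within each allocation period. Pooling the two periods without a period term mixes two randomizations with different assignment probabilities. Usual care then holds a larger share of early enrollees than the mentored arm does, by design and not by chance.

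If the outcome under usual care shifts between periods, the shift is partly attributed to mentoring. It could shift because background diabetes care changes, or because the eligible list yields a different kind of patient as it is worked through. If later background care produces larger falls in HbA1c, the mentored arm looks better than it is; if smaller falls, worse. Adjusting for baseline HbA1c, or modelling change from baseline, removes a shift in starting level but not a shift in the change itself. The 0.20 screen looks at patient characteristics, depends on the data, is described only under stage 2 and does not name period.

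**Working it through.** **The plan's own figures.** U.4.1 states: "To achieve 80% power to detect a 0.8 unit change in HbA1c, with standard deviation of 1.6, a sample of 64 patients per arm". A two-sample t calculation (two-sided 0.05) gives 63.8, hence 64, with power 0.801. Allowing for 10% attrition, 64/0.90 = 71.1, hence 72, as stated. For stage 1, 144/0.84 = 171.4, stated as 171. Usual care: 139 + 56 = 195, as stated.

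**Inputs for the split.** Stage 1: 171 mentored and about 139 usual care (U.4.1). K.3.1 gives 206 mentored instead; usual care is then derived as 492 − 206 − 128 = 158. Stage 2: 72 mentored (K.3.1) and about 56 usual care (U.4.1). Exact 1:1 and 2:1 allocation is assumed.

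**Split by period.** Let *a* be the number per arm at 1:1, followed by 2*b* mentored and *b* usual care. Then *a* + 2*b* = mentored and *a* + *b* = usual care.

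| | 1:1 period | 2:1 period | Early share, usual care | Early share, mentored | Gap |
|---|---|---|---|---|---|
| Stage 1, 171 v 139 | 107:107 | 64:32 | 107/139 = 77.0% | 107/171 = 62.6% | 14.4 points |
| Stage 1, 206 v 158 | 110:110 | 96:48 | 110/158 = 69.6% | 110/206 = 53.4% | 16.2 points |
| Stage 2, 72 v 56 | 40:40 | 32:16 | 40/56 = 71.4% | 40/72 = 55.6% | 15.9 points |

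Combining K.3.1's 206 with U.4.1's 139 gives 16.8 points, so the conflicting stage 1 totals hardly alter the gap.

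**Bias.** Bias = gap × D, where D is the between-period drift in mean HbA1c change. D is not in the documents; 0.1-0.5 units is assumed.

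- Stage 1 (171 v 139): 0.144 × 0.1 = 0.014, up to 0.144 × 0.5 = 0.072.
- Stage 2: 0.159 × 0.1 = 0.016, up to 0.159 × 0.5 = 0.079, which is 9.9% of 0.8.

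**Standard errors.** SE = 1.6/√I. Ignoring period, I = n₁n₂/(n₁ + n₂). Stratified by period, I is the sum of that quantity over the two periods.

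- Stage 1: I = 171×139/310 = 76.67, SE 0.183. Stratified: 107/2 + 64×32/96 = 74.83, SE 0.185. Information loss 2.4%.
- Stage 2: I = 72×56/128 = 31.50, SE 0.285. Stratified: 40/2 + 32×16/48 = 30.67, SE 0.289. Information loss 2.6%.

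**Type I error.** With s = bias/SE, the error is P(|Z + s| > critical value).

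- Stage 1 at 0.025 (U.4.2; taken as two-sided, critical value 2.241), D = 0.5: s = 0.072/0.183 = 0.39, error 0.037. At D = 0.1 it is 0.0255. With 206 v 158 and D = 0.5 it is 0.042.
- Stage 2 at two-sided 0.05, D = 0.5: s = 0.079/0.285 = 0.28, error 0.059. At D = 0.1 it is 0.050.

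**Power for 0.8 units with a period term** (normal approximation, full counts). Stage 1 at 0.025: 98.4% to 98.1%. Stage 2 at 0.05: 80.1% to 79.1%; with 10% attrition, 75.9% to 74.8%.

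**The case against.** The strongest reply is that same-stage usual care is concurrent. At every moment, usual care and mentored patients are randomized side by side, at one ratio or the other. That is correct. A reader might infer from the ratio change that the controls are historical, but only the mix of periods differs. Non-concurrency would come from using stage 1 usual care in the stage 2 comparison, which is a separate and larger matter.

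A reader might also count growing mentor or trainer experience as confounding. The usual care arm receives no added intervention (M.1.1, Arm 1), so such experience changes only mentored outcomes. The pooled difference then averages effects that vary over time, and the arms are not made incomparable.

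Case mix is partly covered by the baseline HbA1c adjustment in stage 1, and by change from baseline and the 0.20 screen in stage 2. Drift in background care and in unmeasured case mix remains.

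Finally, the size is conditional. A drift of 0.8 units, which would give a bias of 0.12-0.13, equals the whole target effect, and nothing in the documents supports it for an enrolment planned at 14-16 months. The switch date and the counts on either side of it are not given either; the split is solved from approximate totals. These points limit the size of the problem. They do not remove the omission.

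**Conclusion.** The point holds as a design-induced bias that is probably modest and is cheap to remove. The ratio change and the missing period term are plain in the text. The gap of about 14-16 percentage points rests on the stated approximate counts and exact ratios. About one-seventh of any between-period drift reaches the estimate. At the assumed 0.1-0.5 units, that is about 0.01-0.08 HbA1c units, at most about 10% of the target. Type I error is then at most about 0.037 in stage 1 (0.042 on K.3.1's counts) against 0.025, and 0.059 in stage 2 against 0.05. If there is no drift, there is no bias. The expectation in U.4.2 that confounding can arise only by chance does not hold once the ratio changes and period is left out.

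A reader might infer that a period term also makes H2 sound if all 195 usual care patients are used. It does not: 139/195 = 71% of them were randomized in stage 1, not against mentoring by former mentees. The H2 text says only usual care, so pooling in that test is inferred from U.4.1.

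**What to change.** Record for each patient the allocation period, before or after the date of the switch, within each stage. The date should be available from the randomization records once the modification is in force.

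Pre-specify period as a fixed effect in the H1 and H2 models, with its interaction with visit wherever change from baseline is tested. In U.4.2, For Stage 1, replace adjustment for baseline HbA1c alone with *adjustment for baseline HbA1c and allocation period*. In the H2 paragraph, add period and period by visit to the listed fixed effects. Delete or qualify the statement that confounding is expected only by chance.

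If usual care is pooled across stages, include stage as well (stage by period), because the 1:1/2:1 indicator alone does not deal with stage 1 controls in H2. State in H2 which usual care patients are used.

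The cost is a few words and one or two model terms. The standard error rises by about 1% and stage 2 power falls by about one percentage point. No patients, visits or measurements are added.
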